Pregnant patients receiving prenatal care at these University of South Florida (USF) and Washington University affiliated locations will be eligible:

- Genesis Healthpark
- South Tampa Center
- Washington University (Barnes Jewish Hospital) in St. Louis

b) Inclusion / Exclusion Criteria

Inclusion Criteria

- Pregnant women, with a singleton gestation
- Ages 18 55
- Able to read and write in English and / or Spanish
- History of spontaneous PTB
- Obesity (≥ 30 kg / m²) vs non-obese groups (18 29.9 kg / m²) defined by first documented body mass index at an office visit
- Gestational age between 12 weeks, 0 days and 24 weeks, 6 days of gestation
- An ultrasound before 24 + 6 weeks gestation to confirm dating and to rule out major fetal anomalies
- Willing to have weekly injections at the physician's office
- The newborn will be enrolled on the mothers consent for chart review only

Exclusion Criteria

- Multifetal gestation
- Known fetal anomaly
- Current progesterone treatment
- Known or suspected breast cancer, other hormone-sensitive cancer, or history of these conditions
- Current or history of thrombosis or thromboembolic disorder
- Current anticoagulation
- Undiagnosed abnormal vaginal bleeding unrelated to pregnancy

- Cholestatic jaundice of pregnancy
- Liver tumors, benign or malignant, or active liver disease
- uncontrolled hypertension (controlled hypertension is eligible)A seizure disorder
- Current or planned cervical cerclage
- Plan to deliver elsewhere

c) Research Design and Methods

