Initial Enrollment: Pregnant patients receiving prenatal care at one of the USF affiliated sites or Washington University in St. Louis sites who report a history of a PTB will be approached by the research nurse. The research nurse will explain the study, review inclusion/exclusion criteria with the patient, and invite interested potential study candidates to sign a medical records release so that records from the previous PTB can be reviewed. If the medical records confirm the birth of a previous PTB was of a live born singleton gestation between the gestational ages of 20 weeks and 36 weeks and 6 days then the patient will be invited to participate in the study. At that time the informed consent form will be thoroughly reviewed with the patient, and if the patient desires to enroll, she will provide informed consent to enroll in the study. Consecutive women with normal BMI or obese women meeting the inclusion criteria will be approached to avoid selection bias.

Randomization: will occur at the time of enrollment. The randomization will be computer generated. Randomization envelopes indicating the randomization arm will be prepared ahead of time and the next consecutive envelope will be used at time of enrollment.

Preparation of study drug: Participants in the 250 mg of 17OHP-C arm will receive 1cc weekly injection of the study drug while the obese women receiving 500 mg of 17OHP-C will receive 2cc weekly injection during the study period. The clinical investigators will not be blinded to the study arm of participant [a) to track which patients receive which dose and b) so that the dose can be given to the treating physician should an adverse event occur], but the lab performing the pharmacokinetics studies will be blinded.

Administration of study drug: Administration of study drug will be performed by clinic staff in the office to ensure medication compliance. Although the patients will be enrolled into the study from as early as 12 weeks in preparation for the intervention, study medications will not be started until at least 16 weeks. The medication will be administered from between 16+0 weeks and 24 +6 weeks until 36 + 6 weeks gestation or until in preterm labor with advanced dilatation/delivery.

If the participant has already received the first prescription but has not yet taken any doses they would still be eligible to participate. They would not be able to return the medication to the pharmacy or

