donate the medication. They could use their medication and then the remainder of the medication would be provided by the study.

Timeline of study visits: At the enrollment visit, a maternal blood draw to determine baseline 17P levels will be completed. Participants will then have the weekly visits with their obstetric care provider for the administration of the 17OHP-C injections, with the dose determined by the study arm to which they were allocated. They will also continue to have their scheduled prenatal care with their obstetric provider.

In addition to the routine prenatal care there will be Pharmacokinetic studies as described below.

Pharmacokinetic studies: Sampling schedule in order to investigate the pharmacokinetics of 250 mg 17OHP-C weekly as compared to 500 mg 17OHP-C weekly in obese women as well as 250 mg in non-obese women will be performed as follows:

- Using principles described by Caritis et al., four completed weeks of 17OHP-C therapy is required prior to sampling anticipating that steady state will be achieved by this time point.
- Follow-up sampling will be performed at these three time points:
- Sample #1: 20 22 weeks gestation
- Sample #2: 27 29 weeks gestation
- Sample #3: 34 36 weeks gestation

The blood draws will occur immediately before the weekly injection in order to obtain trough 17-OHPC levels.

Blood will be stored for future analysis into the use of 17OHP-C and preterm birth. The blood stored for future research will not contain any identifying information and will only contain the individual patient randomization number and the time (gestational age) when it was drawn.

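### Opening the envelope at enrolment, up to 4 or more weeks before the first injection, puts avoidable pre-dose losses after allocation in the only randomised comparison

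*Combined protocol and SAP*

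**What the plan says.** Under section c) Research Design and Methods, the Randomization paragraph states "Randomization: will occur at the time of enrollment" and adds that "the next consecutive envelope will be used at time of enrollment". Section b) Inclusion / Exclusion Criteria sets the entry window: "Gestational age between 12 weeks, 0 days and 24 weeks, 6 days of gestation".

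The paragraph on administration of study drug confirms that women may be "enrolled into the study from as early as 12 weeks", but that "study medications will not be started until at least 16 weeks". The first dose may fall anywhere from 16+0 to 24+6. The pharmacokinetic section adds that "four completed weeks of 17OHP-C therapy is required prior to sampling", and places sample #1 at 20-22 weeks.

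On blinding, the paragraph on preparation of study drug states: "The clinical investigators will not be blinded to the study arm of participant". The arms receive 1 cc or 2 cc weekly. The laboratory is blinded.

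Section e) Data analysis plans 21 obese women per arm with a single 10% dropout allowance. It sizes the trial at alpha 0.025. It then makes unadjusted p<0.05 the primary significance criterion and p<0.025 the secondary one. It defines no analysis set, no rule for women randomised but never dosed, and no method for missing troughs.

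**The concern.** The primary outcome is the trough level on treatment. A woman who leaves between allocation and first injection cannot supply one, yet she already counts as randomised. She is then missing from the comparison for a reason that arose after her arm was known.

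Two things are at stake. The first is bias: staff know the allocation during the wait, so losses could differ between the 250 mg and 500 mg arms. That contrast is the only randomised one in the study, because the non-obese group is not randomised. The second is precision: with 21 women per arm, each loss is 1/21 = 4.8% of an arm, and the 10% allowance (0.10 × 21 = 2.1 women) has to cover losses before and after the first dose.

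**Working it through.** **Length of the gap**

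- Minimum for a woman enrolled at 12+0: 16+0 − 12+0 = 4 weeks.
- Sample #1 at 20-22 weeks after four completed weeks of therapy implies a start at about 16-18 weeks (20 − 4 and 22 − 4). That makes the gap about 4-6 weeks for a woman enrolled at 12+0.
- Her first valid trough comes at least 4 + 4 = 8 weeks after allocation.
- A woman enrolled at 16+0 or later need have no gap. The documents do not say what share will enrol before 16 weeks.

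**Reproducing the planned 21 per arm**

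Inputs from the sample size section: means 6.4 (SD 4.0) and 11.0 (SD 5.0), alpha 0.025, power 0.80, dropout 10%. A two-sided test is assumed, because sidedness is not stated.

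- Difference: 11.0 − 6.4 = 4.6.
- SD: √((5² + 4²)/2) = 4.528.
- n = 2 × [4.528 × (2.241 + 0.842)/4.6]² = 18.42, so 19 evaluable per arm.
- With dropout: 18.42/0.9 = 20.5, so 21 per arm.

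The planned figure reproduces at power 0.80. The printed beta of 0.02 does not match it (power 0.98 would need 36 evaluable per arm).

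**Power as evaluable women fall**

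Noncentral t with 2n − 2 degrees of freedom and noncentrality 4.6/(4.528 × √(2/n)). For example, n = 19 gives 4.6/1.469 = 3.13 on 36 degrees of freedom.

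| Evaluable per arm | Lost from 21 | Power, alpha 0.025 | Power, p<0.05 |
|---|---|---|---|
| 21 | 0 | 0.83 | 0.90 |
| 19 | 2 | 0.78 | 0.86 |
| 18 | 3 | 0.76 | 0.84 |
| 17 | 4 | 0.73 | 0.82 |
| 16 | 5 | 0.70 | 0.79 |

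The 0.78 at 19 women is not an effect of early randomisation. It reflects the t distribution at the planned evaluable number; the normal approximation gives 0.81 there.

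**Illustration with an assumed loss rate**

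The documents give no pre-dose loss rate. If 5%, 10% or 15% were lost before dosing, in addition to the full 10% dropout, the evaluable number per arm would be:

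- 21 × 0.9 × 0.95 = 18.0
- 21 × 0.9 × 0.90 = 17.0
- 21 × 0.9 × 0.85 = 16.1

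Power would then run from 0.76 down to 0.70 at alpha 0.025, and from 0.84 down to 0.79 at p<0.05. If the stated 10% already includes pre-dose loss, about 19 women remain and there is no further cost.

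**The case against.** The strongest reply is that the loss is hypothetical. No rate is given, the 10% allowance is not restricted to on-treatment loss, and at the primary criterion of p<0.05 the trial keeps power above 0.80 with four losses per arm. Both arms receive free active drug and the assay is blinded, so differential loss is conjecture. This stands as a limit on the size of the point. It does not remove the point: a blinded laboratory protects the measurement, not retention, and the risk of differential loss does not depend on the alpha chosen.

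A reader might also infer more than the documents support:

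- **That an anomaly or cerclage found during the wait leaves a woman without a trough.** Both are entry exclusions, but nothing says whether a woman in whom either arises later is dosed. Only pregnancy loss and withdrawal clearly prevent a trough.
- **That the anomaly scan follows allocation.** The criterion reads "An ultrasound before 24 + 6 weeks gestation to confirm dating and to rule out major fetal anomalies". It is an inclusion criterion, and criteria are reviewed before consent, so the plain reading puts it before the envelope. For early enrollees the wording leaves the order open, but does not establish that the scan comes later.
- **That the wait is nearly 13 weeks.** The outer limits allow 24+6 − 12+0 = 12 weeks 6 days, but the schedule for sample #1 points to about 4-6 weeks.

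**Conclusion.** The point holds as a design weakness of unknown size that is cheap to remove. For women enrolled before 16 weeks, allocation precedes dosing by an avoidable interval, up to at least 4 weeks for a woman enrolled at 12+0. Pregnancy loss or withdrawal in that interval is a post-randomisation loss with no on-treatment trough.

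The main reason to act is to protect the one randomised comparison; the gain in power is modest. A reader might conclude that the trial is left underpowered, but the documents do not support that. The fall to 0.70 uses alpha 0.025 and an assumed loss that leaves 16 women per arm; at the primary criterion the same 16 women give 0.79. These figures rest on the protocol's means and SDs, a two-sided t-test and equal losses in the two arms.

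**What to change.** Keep consent and the baseline draw at enrolment, under a study ID. Open the next consecutive envelope at the first-injection visit, after eligibility is rechecked against the existing criteria. Count the 42 obese women as randomised at that visit. The timing of treatment does not change, and no visit is added because injections are already given in the office.

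The costs are small but real. A few consented women will never be randomised, so consents will somewhat exceed 42. The baseline sample needs a label that does not depend on the randomisation number, because the pharmacokinetic section identifies stored blood by that number and gestational age.

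The change is partial. Losses between the first dose and the first trough remain, and a woman can still withdraw on learning her arm, although the time in which she could do so before dosing is shorter.

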Among women with a history of a spontaneous PTB, 17OHP-C has been shown in a randomized trial to decrease the risk of a subsequent PTB by 33%. In this study including 463 women, the number needed to treat to prevent one PTB prior to 37 weeks was only 5 to 6 women. ¹⁷ In addition to effectively reducing the recurrence of PTB, mathematical modelling has demonstrated that administration of 17OHP-C to women with a prior spontaneous PTB could lead to future cost savings.^{18, 19} The individual and societal benefits of 17OHP-C are clear. However, questions remain about optimal dosing of 17OHP-C among obese women. As the prevalence of obesity in the United States exceeds 35%, optimizing interventions to prevent PTB in this population has significant public health implications.

Obesity causes several physiological changes than can impact medication pharmacokinetics. Some changes include increased blood volume and increased cardiac output which can lead to varied distribution patterns and potentially a change in medication absorption.^{20, 21} Caritis et al. demonstrated that body mass index (BMI) was inversely correlated with trough plasma 17OHP-C concentrations and the area under the plasma concentration versus time curve. These data suggest that higher dosing may be needed for obese patients.²² A similar conclusion was reached in a secondary analysis of a Maternal-Fetal Medicine Unit Trial. Among 443 women, treatment with 17OHP-C in obese women or with a weight of > 165 pounds did not appear to decrease the rate of PTB.²³ Moreover, additional studies have shown that low plasma 17OHP-C levels ²⁴ and a maternal pre-pregnancy BMI of $\ge 25 \text{ kg/m}^2$ are associated with higher rates of spontaneous PTB.²⁵

Conversely, other retrospective studies report that spontaneous PTB rates among normal weight as compared to obese women are similar suggesting that current 17OHP-C dosing guidelines are sufficient.²⁶ Literature supporting optimal dosing of 17OHP-C for obese patients is lacking and current clinical studies report conflicting information.

C. Study Design

Prospective three arm study of women with a prior spontaneous PTB. Non-obese women will receive the standard 250 mg weekly dose of 17 OHP-C while obese women will be randomly assigned to the standard (250 mg) or higher dose (500 mg). The resulting three groups will consist of:

- 1. Normal weight women on 250mg 170HPC
- 2. Obese women on 250mg 170HPC
- 3. Obese women on 500mg of 170HPC
- a) Subjects

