Data Collection: Socio-demographic data of all enrolled subjects will be collected. These will include: maternal age, height, weight and body mass index (BMI), smoking, alcohol, socioeconomic status, ethnicity, parity and coexisting maternal medical disorders, previous and current pregnancy information, concomitant medications, and ultrasound examinations. While having the injections the site of the injection administration will be collected, and date and time of administration. Following delivery information from the delivery will be collected (pregnancy complications, type of labor, mode of delivery, delivery complications, gestational weight at delivery, birth weight, Apgar scores, cord blood gases, nursery admission and discharge information). Newborn outcome (respiratory distress, intraventricular hemorrhage, hypoglycemia, necrotizing enterocolitis, periventricular leukomalacia, seizures) and including any neurological assessment will also be collected.

d) Outcomes

- a. Primary Outcome: Mean trough levels of 17-OHPC in the three groups.
- b. Secondary outcomes of interest:
 - mean 17OHP-C plasma concentrations,
 - average peak concentration (Cmax)
 - half-life of 170HP-C
 - absorption, metabolism, volume of distribution, apparent clearance of 170HP-C
 - Gestational age at delivery
 - Preterm birth <37, 34, 32, 28 weeks

e) Data analysis

a. Sample Size Calculation:

We estimate the sample size for the study based on the primary aim and a number of assumptions:

- Trough concentrations (before next dose) for analysis²⁸
- Mean trough in normal weight women=11.0ng/mL (sd 5.0)²⁸
- Mean trough in obese women receiving 250mg =6.4 ng/mL (sd 4.0); assumed to be the dose below which efficacy is suboptimal²⁸
- Mean trough in obese women receiving 500mg =11.0 (sd 5.0); double dose assumed to return concentration to that for 250mg dose in normal weight women
- Alpha=0.05/2=0.025 (Bonferroni correction for 2 comparisons [normal 250mg vs obese 250mg and obese 500mg vs obese 250mg])
- Beta=0.02, Power=0.80
- Drop out rate=10%.

Sample size:

Based on the above assumptions we will enroll a total of 63 women with a prior history of spontaneous PTB (21 non-obese women, and 42 Obese women randomly assigned to 250 mg (n=21) or 500 mg (n=21) of weekly 17 OHP-C.

The breakdown of enrollment between University of South Florida affiliated sites and the Washington University in St. Louis affiliated sited is:

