USF - 28 participants (6 non-obese women, and 22 Obese women randomly assigned to 250 mg (n=11) or 500 mg (n=11)

Washington University in St. Louis – 35 participants (15 non-obese women, and 20 Obese women randomly assigned to 250 mg (n=10) or 500 mg (n=10)

b. Data Analyses

The Student's t-test or Wilcoxon rank sum test will be used to compare levels of 17OHP-C and other continuous outcomes in obese women on 250 mg to obese women on 500 mg and to non-obese women on 250 mg. Categorical outcomes will be compared using the chi-squared or Fisher's exact test as appropriate.

Because this is a pilot study, the primary criterion for significance (p<0.05) will not be adjusted for multiple comparisons, in order the avoid missing a potentially significant effect. However, the secondary criterion will be P<0.025 (adjusted for the 2 comparisons).

f) Feasibility

- Potential Pitfalls: There is the potential to lose women to follow up due to the prospective design of the study. Several methods to improve study enrollment will be employed. First, 17OHP-C free of charge to the patients will be an incentive for enrollment. Second, the use of dedicated study staff will provide long-term continuity, and with whom the patient will develop rapport.
- b. *Training*: Before enrolling patients, all study staff will be trained on the study protocol, inclusion criteria, exclusion criteria, specimen collection, data collection and entry.
- c. *Leadership*: Successfully completing a prospective randomized trial is a challenging task. The experienced leadership of [name], [name] and [name] will ensure that obstacles encountered during the course of the trial are addressed in a constructive manner to continue moving forward with the project in a timely manner.

g) Timeline

Our goal is to complete the study within 1.5 years (18 months) including time to obtain the needed IRB approval, finalize protocol, recruit and start data analysis.

Study Timeline

Project Period (months)	0 - 3	4 - 16	16 - 18
Protocol development & IRB			
Subject recruitment			
Data collection & management			
Data analysis			
Drafting of manuscript & reports			

h) Ethical Aspects of the Proposed Research

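### The randomised 500 mg versus 250 mg trough comparison makes no use of baseline BMI; adjusting for it would gain a little precision, and the unadjusted test is valid without it

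*Combined protocol and SAP*

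**What the plan says.** The outcome is given in section C.d as "Primary Outcome: Mean trough levels of 17-OHPC in the three groups". The only analysis of levels is in section C.e (Data Analyses): "The Student's t-test or Wilcoxon rank sum test will be used to compare levels of 17OHP-C and other continuous outcomes". It is applied to obese 250 mg versus obese 500 mg and to obese 250 mg versus non-obese 250 mg. No regression, covariate or site term appears anywhere, and no rule is given for choosing between the two tests.

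The Background reports that BMI "was inversely correlated with trough plasma 17OHP-C concentrations and the area under the plasma concentration versus time curve". The inclusion criteria form the groups from BMI "defined by first documented body mass index at an office visit", with no upper limit for obese women, and section C.c (Data Collection) lists BMI among the baseline data. The Randomization paragraph describes computer-generated consecutive envelopes and no stratification by BMI. The enrolment targets by centre are 11:11 and 10:10 for the two obese arms. For the non-obese group they are 6 at the University of South Florida (USF) and 15 at Washington University.

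**The concern.** The trial rests on the premise that BMI lowers trough level. The plan uses BMI to form groups and then ignores it within the obese women, whose BMI can run from 30 upwards. Any trough variation due to BMI then stays in the error term of the one randomised comparison. With 21 women per arm, a chance difference in BMI between the arms is handled neither by design nor by analysis. At stake are the width of the confidence interval and a few points of power, at no cost in new data.

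Site is a lesser matter. The planned targets balance it across the randomised arms but not across non-obese versus obese 250 mg.

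**Working it through.** **1. The plan's own figure.** Section C.e (Sample Size Calculation) gives 6.4 (SD 4.0) and 11.0 (SD 5.0) ng/mL, alpha 0.025 (taken as two-sided) and power 0.80.
- n = (4.0² + 5.0²) × (2.241 + 0.842)² / 4.6² = 18.4, so 19 evaluable per arm.
- 19 × 1.10 = 20.9, so 21. The stated size reproduces, and it assumes an unadjusted comparison.

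**2. What the documents say about BMI and trough.** No correlation is given. The planning means imply only the share explained by the obese/non-obese split at 250 mg, where p is the obese fraction:
- R² = p(1−p)·4.6² / [p(1−p)·4.6² + (1−p)·25 + p·16].
- At p = 0.5 this is 0.205. At p = 0.35 (the Background's US prevalence figure) it is 0.181.

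This is variation between the groups. It says nothing direct about variation among women who are all obese, so a range of 0–10% is assumed below.

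**3. Chance imbalance.** With 21 per arm and simple randomisation, the standard error of the difference in mean BMI is √(2/21) = 0.31 SD. A difference beyond 0.5 SD has probability of about 0.10 (0.5/0.309 = 1.62). At R² = 10% (r = 0.316; pooled SD √(41/2) = 4.53) it would shift the estimate by 0.316 × 0.5 × 4.53 = 0.7 ng/mL, in either direction.

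**4. Power for 500 versus 250 mg, by simulation.** Assumptions not in the documents: 19 per arm; the planning SDs are single-trough SDs; within-woman correlation 0.5; Samples #1/#2/#3 missing in 30%/5%/15%; R² is BMI's share of single-trough variance within arm. Each woman contributes the mean of her available troughs. The regression has group, BMI and site, with HC2 standard errors.

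| Data | Criterion | t-test | Wilcoxon | Regression, R² 0 | R² 5% | R² 10% |
|---|---|---|---|---|---|---|
| Normal, up to 3 troughs | p<0.05 | 0.95 | 0.93 | 0.94 | 0.955 | 0.965 |
| Normal, up to 3 troughs | p<0.025 | 0.90–0.91 | 0.88–0.89 | 0.89 | 0.92 | 0.93 |
| Normal, 1 trough | p<0.025 | 0.78 | 0.75 | 0.76 | 0.79 | 0.82 |

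- Against the t-test under normality, break-even is at R² of about 2–3%.
- At R² = 10% the SD of the estimate falls from 1.235 to 1.155. Since (1.155/1.235)² = 0.875, the variance falls by about 12%.
- If Sample #1 is missing in 10% or 67% of women, the p<0.025 figures at R² = 10% are 0.94 or 0.92, against 0.91 or 0.89 for the t-test.
- Type I error of the regression is 0.047–0.055 at 0.05 and 0.023–0.028 at 0.025.

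**5. Skewed data.** A normal model with mean 6.4 and SD 4.0 puts Φ(−1.6) = 5.5% of troughs below zero, so skew is plausible. With lognormal troughs at the same means and SDs, p<0.025, R² 0–10% (now on the log scale) and up to three troughs:
- planned Wilcoxon test: 0.95–0.96
- untransformed regression: 0.90–0.935
- regression on each woman's mean log trough: 0.97–0.99

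**6. Site.** USF supplies 11/21 of obese 250 mg women and 6/21 of non-obese women, a gap of 5/21 = 0.24. Each 1 ng/mL of true site difference would shift that contrast by 0.24 ng/mL, or 0.24/4.6 = 5% of the planned difference. In the randomised arms the planned gap is 11/21 − 11/21 = 0.

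**The case against.** The strongest reply is that the planned test is valid, matches the sample-size method and, on these assumptions, already has power above the intended 0.80 when a woman's troughs are averaged. At the primary p<0.05 the gain is about 0.5–2 points for R² of 5–10%, and it becomes a loss of about 1 point if BMI explains nothing. This stands, and it limits the weight of the point.

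The plan's Wilcoxon option also protects against skew, and replacing it with an untransformed regression could lose power (step 5). This stands too, and the fix has to respect it.

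Three stronger readings are tempting and not supported:
- **BMI explains about 20% of the variance in the randomised comparison.** The 18–21% is the obese/non-obese contrast itself. Values such as 25% should be treated as an extreme: with within-woman correlation 0.5, they would mean that BMI explains 0.25/0.5 = half of all stable between-woman variation among obese women.
- **The randomised result is biased.** Randomisation makes BMI imbalance a matter of chance, so the unadjusted estimate is unbiased over repeated allocation.
- **Site confounds the non-obese contrast.** The targets are unbalanced, but no site effect is documented, so this is only a possibility.

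Pilot status does not answer the point. The plan relaxes its alpha so as not to miss an effect, and using a predictor it already names serves that aim without loosening the error rate.

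**Conclusion.** The point holds as a modest improvement, with moderate confidence. The plan leaves a named, collected predictor of trough out of its only randomised comparison. The cost is precision and protection against chance imbalance. For a within-obese R² of 0–10%, adjustment changes power by between about −1 and +2 points at p<0.05 and between about −1 and +3 points at p<0.025. With one trough per woman the range at p<0.025 is about −2 to +4 points. These figures rest on the assumed R², within-woman correlation and missing rates, and on normal data; none of these is in the documents. A reader might infer that the trial is underpowered or its primary test invalid; neither follows, since the stated sample size reproduces without any adjustment.

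**What to change.** **Obese 500 versus 250 mg.** Make the primary analysis a linear regression of each woman's mean qualifying trough on dose group and continuous baseline BMI (the value used for eligibility), with HC2 standard errors because the planning SDs differ. Site may be added but is optional, as the planned arms are balanced by site. A qualifying trough is one taken after the four completed weeks of therapy that the pharmacokinetic section requires. The plan must state this per-woman value anyway, since it schedules up to three samples and does not say how they combine.

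**Scale.** Fix it before levels are linked to dose group. Use ng/mL where the t-test would have applied. Where the Wilcoxon test would have applied, use the mean of log troughs, reported as a ratio of geometric means. In either case report unadjusted means in ng/mL for all three groups and keep the planned t-test or Wilcoxon test as a sensitivity analysis.

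**Non-obese versus obese 250 mg.** Do not adjust for BMI, which defines these groups. Keep the planned test and add a site-adjusted estimate as a sensitivity analysis.

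**Cost.** Wording only, with no new data or women. If BMI and site explain nothing, about 1 point of power is lost in the randomised comparison (about 2 with one trough per woman). If the log scale is used, the effect is a ratio and not a difference in means.
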